Justification to include smokeless tobacco and e-cigarette users: We will include users of smokeless tobacco or e-cigarettes given the high prevalence of e-cigarette and smokeless tobacco products among young adults (26-28). As noted above, urine cotinine will be used to biochemically confirm the subjects' nicotine consumption and smoking status and used as a covariate in all analyses if required.

Subject sampling to account for sex, race, dependence symptoms, and smoking frequency: We are planning to enroll Caucasian and African-American smokers while maintaining an approximately equal male-to-female ratio.

We will create dichotomous variables to be used as a covariate to match groups on race (European American and African American) and sex because of the potential influence of race and sex on smoking behavior and nicotine pharmacokinetics (22, 29). We will also control for differences in the frequency of smoking because it may influence the behavioral effects nicotine (30-32); a continuous variable based on the reported smoking frequency (cigs per day) will be used as a covariate in the analyses if required.

8: Recruitment:

Hundred subjects will be recruited. The goal is to have 70 completers, 35 menthol and 35 non-menthol cigarette smokers.

9. Research Plan:

A. Overview

Experimental Summary: Subjects will complete five separate experimental sessions on five separate days with each session beginning around 8 AM (Fig 2). Each session (1 to 15 days apart) will include one infusion condition that will be either saline or nicotine at four different infusion rates. The five infusion conditions will be assigned randomly to one of the five experimental sessions. All infusions will last 10 minutes and be controlled by two infusion pumps, a saline infusion pump and a nicotine infusion pump. The 0.24 mcg/kg/s condition will include a 1 minute infusion of nicotine followed by a 9 min infusion of saline; the 0.096 mcg/kg/s condition will include a 2.5 minute infusion followed by a 7.5 min infusion of saline; the 0.048 mcg/kg/s condition will include a 5 min infusion of nicotine followed by a 5 min infusion of saline; the 0.024 mcg/kg/s condition will include a 10 min infusion of nicotine and no infusion of saline; and the placebo condition will include a 10 min infusion of saline and no

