Positive subjective effects of nicotine will be assessed with the “Like the Drug Effects” and “Good Drug Effects” items from the DEQ, consistent with the FDA Guidance on abuse potential assessment (10). These items have been shown to correlate with the abuse potential of drugs of abuse. Effects will be tested using linear mixed effects models with peak change on each DEQ item as a response variable, cigarette-preference (menthol vs. non-menthol) as a between-subject factor, nicotine delivery condition as a within-subject factor and their interaction. Period effects will be controlled for by including test day as an additional predictor in the models. Random effects for subject and condition within subject will be used to account for correlations between repeated measures. Because of the potential skewed distributions of the subjective effects data, transformations will be applied as necessary. We will evaluate the main and interactive effects of menthol cigarette preference and delivery rate. We anticipate statistically significant main effects of menthol-preference, nicotine delivery rate and a significant interaction between menthol-preference and nicotine delivery rate. To better understand the dose effects of nicotine delivery rate and whether they are moderated by menthol preference, we will construct specific contrasts among the four doses to test whether there is an indication of significant linear, quadratic, linear on log-scale or sigmoidal dose-response relationships across, or within menthol-preference groups. The possible dose-response curves identified by the specific mean contrasts will be compared by fitting linear and non-linear (as necessary) dose-response models with continuous dose and selecting the best-fitting model by the Akaike’s Information Criterion (AIC).

To test for an effect of delivery rate on smoking urges, assessed by the BQSU (Factor 1 and 2) scores, we will use similar modeling approach described for subjective effects but we will also include time as a within-subject factor with outcomes for minute 0, 10, 30, 60 and 120. We anticipate a significant main effect of menthol-preference, nicotine delivery rate and potentially a significant interaction between menthol-preference and nicotine delivery rate.

Rationale for sample size:

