The study will have 80% power to detect large effect sizes ($f=0.4$) for the main effect of menthol with 31 individuals per group at 0.025 significance level (Bonferroni-adjusted for two outcome measures) for each hypothesis. Our previous study showed large magnitude effects of preference for mentholated cigarettes on feeling good and stimulated effects ($d=0.8$ or larger, corresponding to $f=0.4$ or larger). Our pilot data also showed large effects of nicotine ($f>0.6$) and the rate of infusion effects are expected to be similarly strong (42, 48, 54, 83). With 28

individuals per group we have 80% power to detect effect sizes of this magnitude ($f>0.5$) for the within-subject effect of nicotine delivery rate and in the interaction between nicotine delivery rate and menthol. To account for 20% drop-out rate, we will recruit 35 participants for each group.

11. Risks and benefits:

Potential risks

There are potential risks, discomforts and inconveniences associated with the participation in this study. These may be due to nicotine administration, blood drawing, and other study procedures.

- 1) The administration of nicotine may cause cardiovascular, autonomic, and gastrointestinal complications. Large doses of nicotine may cause nausea, vomiting, abdominal pain, hypersalivation, diarrhea, dizziness, confusion, hearing and vision problems, syncope, seizures, hypotension, irregular pulse, and death. However, these toxic effects occur at doses 10-20 times that which will be used in our study. Other potential risks from this study include administering a drug that has addictive potential. However, since only subjects with a history of cigarette use are to be included, we will not be exposing subjects to the risks of nicotine for the first time. Additionally, we are not enrolling subjects who are seeking treatment to quit smoking. Over the last 5 years, we have administered nicotine intravenously to more than 100 smokers and have not encountered any adverse events from nicotine.
- 2) Blood Drawing: Subjects will have less than 300 ml of blood drawn as a result of their participation in the study. Blood drawing can cause some pain and may result in bruising.

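### With one DEQ peak per subject and condition, the condition-within-subject random effect is redundant with residual error, so standard errors for the four-rate contrasts rest on an unstated equal-variance, equal-correlation assumption

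*Combined protocol and SAP*

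**What the plan says.** Section 10 (Data analysis methods) analyses Drug Liking and Good Drug Effects with "linear mixed effects models with peak change on each DEQ item as a response variable". Menthol preference is the between-subject factor, delivery condition the within-subject factor, and test day is added for period effects. The dependence structure is given in one sentence: "Random effects for subject and condition within subject will be used to account for correlations between repeated measures". No covariance type, unequal-variance option, robust standard error or degrees-of-freedom method is named.

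The design in Section 9.A fixes how many observations that model has. "Each session (1 to 15 days apart) will include one infusion condition that will be either saline or nicotine at four different infusion rates", and "The five infusion conditions will be assigned randomly to one of the five experimental sessions". No condition is repeated.

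Inference on the shape of the curve follows from the same model: "we will construct specific contrasts among the four doses", covering linear, quadratic, log-linear and sigmoidal shapes. The one distributional safeguard is this: "Because of the potential skewed distributions of the subjective effects data, transformations will be applied as necessary".

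For smoking urges (BQSU) a similar model is planned, but there "we will also include time as a within-subject factor with outcomes for minute 0, 10, 30, 60 and 120".

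**The concern.** A random effect for condition within subject is useful when each subject has several observations under each condition. The BQSU model has them. The DEQ peak model does not: it has five numbers per subject, one for each condition. The extra term then adds nothing beyond a random intercept, and all contrasts share one pooled within-subject variance.

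Pooling is harmless if the conditions have equal spread and equal correlations. On a 100 mm scale anchored at not at all, it is plausible that saline peaks cluster near zero and that ratings at the fastest rate spread widely. A contrast weighted towards the fastest rate would then be tested with a standard error that is too small. The linear-in-rate contrast is of this kind, because 0.24 mcg/kg/s lies far from the other three rates. These contrasts decide which dose-effect shapes are carried forward, and the dose-effect curve is the study's primary aim.

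**Working it through.** **The plan's own figure.** The stated power is "80% power to detect large effect sizes ($f=0.4$) for the main effect of menthol with 31 individuals per group at 0.025 significance level". The noncentral F with 1 and 60 df at f = 0.4 (d = 0.8), alpha 0.025 two-sided, gives power 0.8001 at 31 per group, so the figure reproduces. It concerns a between-subject comparison. With complete data that comparison uses each subject's mean over conditions, so the present point leaves it alone.

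**Step 1: identifiability.** For one subject's five peaks, with scalar variance components,

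V = σ²(subject)·J + [σ²(condition) + σ²(residual)]·I,

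where J is the 5x5 matrix of ones and I the identity. Every diagonal element is the sum of the three components and every off-diagonal element is σ²(subject). That is two distinct moments for three parameters; the information matrix has rank 2. Only the sum of the last two components can be estimated, and the fitted covariance is compound symmetry.

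**Step 2: standard error of a contrast.** For contrast weights v and true covariance Σ:

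- true variance is proportional to v′Σv;
- the compound-symmetry model uses m·v′v, with m = average variance − average covariance over the five conditions;
- SE ratio = √(m·v′v / v′Σv);
- actual alpha ≈ 2[1 − Φ(2.257 × ratio)], where 2.257 is the two-sided 0.025 critical value of t on 54 × 4 = 216 df. With a ratio of 1 this approximation gives 0.024.

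Inputs from the documents: rates 0.024, 0.048, 0.096 and 0.24 mcg/kg/s; alpha 0.025; 35 per group less 20% = 28, so 56 completers. Assumed, because the documents give none: SDs by condition (saline first, then slowest to fastest), correlation 0.5, no transformation, and saline included in the model.

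**Step 3: linear in rate.** The mean rate is 0.102, so v = (0, −0.078, −0.054, −0.006, 0.138) and v′v = 0.02808. With correlation 0.5, v′Σv = ½Σ(vᵢsᵢ)² + ½(Σvᵢsᵢ)².

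- SDs 12/16/18/20/24: m = 340 − 160 = 180. Model: 180 × 0.02808 = 5.054. Truth: ½(13.486) + ½(0.972²) = 7.215. Ratio √(5.054/7.215) = 0.84; alpha 0.059.
- SDs 8/14/18/22/28: m = 370.4 − 156.2 = 214.2. Model: 6.015. Truth: ½(17.085) + ½(1.668²) = 9.934. Ratio 0.78; alpha 0.079.
- Equal SDs: ratio 1.00; alpha 0.024.

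**Step 4: linear in log rate.** v = (0, −1.096, −0.402, 0.291, 1.207), v′v = 2.904.

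- Milder SDs: √(522.7/666.5) = 0.89; alpha 0.046.
- Wider SDs: √(622.0/890.6) = 0.84; alpha 0.059.

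**Step 5: simulation.** Simulated trials with 56 subjects, which estimate the pooled variance instead of taking it as known, agree or run slightly higher.

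| Contrast | Milder SDs | Wider SDs | Equal SDs |
|---|---|---|---|
| Linear in rate | about 0.06 | 0.080 to 0.086 | 0.024 |
| Linear in log rate | 0.045 to 0.048 | 0.062 to 0.066 | 0.024 |

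Contrast-specific standard errors, which an unstructured covariance delivers, held about 0.025 throughout.

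**Step 6: sensitivity.**

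- Unequal correlations alone are enough. With equal SDs and correlation 0.8 raised to the distance between conditions, the linear-in-rate ratio is 0.83 and alpha 0.061.
- The omnibus rate test is less affected: 0.030 to 0.046 over four assumed departures, with almost the same range for the rate-by-menthol interaction.
- If saline were left out of the model, m becomes 389 − 188.7 = 200.3 (milder SDs) or 447 − 205.7 = 241.3 (wider SDs). The linear-in-rate ratios are then 0.88 and 0.83, and alpha about 0.046 and 0.062. The problem shrinks but remains.
- A slowest-rate versus saline comparison would err the other way. Its standard error would be √(360/208) = 1.32 to √(428.4/148) = 1.70 times too large, which is conservative.

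**The case against.** **The redundancy is harmless in itself.** This is true. If variances and correlations are equal across conditions, the random-intercept model is correct. The documents report no SD or correlation by condition, so every size above is assumed.

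**The plan already provides for transformation.** This is the strongest objection. If spread rises with the mean, a transformation can remove much of the inequality. In an illustration with gamma-shaped peaks whose SD is proportional to the mean, the ratio for 0.24 versus 0.096 moves from 0.82 untransformed to 0.87 with a square root and 0.95 to 0.96 with log(1 + x). But the step is conditional, has no stated criterion, is aimed at skew, and gives a result that depends on the transformation chosen. It reduces the risk and does not replace a covariance specification.

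**The sentence might mean correlated condition effects with an unstructured matrix.** The residual would still not be separable (16 parameters for 15 moments), but the marginal covariance would be free and equal variances would not be imposed. The text does not say this. If it is what was meant, writing it down settles the point.

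**Stronger readings that the documents do not support.** A reader might infer that the threshold estimate is lost because the slowest rate is tested against saline with an inflated standard error. Section 10 does not list that contrast. Section 4 takes the threshold from the dose-effect curve, and Section 10 compares curve models by AIC. A reader might also infer that the menthol main effect or the 31 per group is compromised; with complete data neither is.

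**Conclusion.** The point holds in conditional form. It is certain from the design that a scalar condition-within-subject variance cannot be estimated in the DEQ peak model, and that on the ordinary reading the model assumes one variance and one correlation across the five conditions. It is not established that the standard errors will be wrong. That requires variances or correlations that differ by condition and that remain unequal after any transformation.

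If they do differ as assumed here, the linear-in-rate contrast runs at roughly two and a half to three and a half times its nominal 0.025 (about 0.06 to 0.09), and the log-linear contrast at roughly two to two and a half times (0.045 to 0.066). The BQSU model is not open to the same criticism, since its repeated times make the condition-within-subject effect estimable. The change is worth making before analysis because it protects the contrasts that serve the primary aim at almost no cost.

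**What to change.** In Section 10, for the two DEQ peak-change models:

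- replace the two random effects with an unstructured 5x5 within-subject covariance over the five conditions;
- use Kenward-Roger degrees of freedom;
- apply this after any transformation, on the scale that is analysed;
- name heterogeneous compound symmetry as the fallback if the unstructured fit does not converge.

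Keep the random effects for subject and condition within subject in the BQSU model, and state there that they apply to that model.

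The cost is one or two sentences and standard software. The unstructured matrix has 15 parameters (5 × 6 / 2), which 56 to 70 subjects can support. The downside is a very small loss of power if the variances are in fact equal: 41% against 43% in one simulated check with equal SDs.

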Specific Aim: To determine the dose-effect curves for positive subjective effects (drug liking and good drug effects) and alleviation of smoking urges, as a function of nicotine delivery rate in menthol and non-menthol cigarette preferring smokers.

Hypothesis #1A: Positive subjective effects of nicotine will gradually decline with slower delivery rates, with minimal effects of nicotine delivery rate on urges to smoke.

Hypothesis #1B: Non-menthol smokers, compared to menthol smokers, will have greater responses to nicotine for these outcomes as reflected by a leftward shift in dose-effect curves.

Exploratory Aim #1: To explore the dose-effect curves of nicotine delivery rate for a) reinforcement (assessed with the monetary value of the dose from the Multiple-Choice Procedure (6), b) heart rate and blood pressure, and c) tobacco withdrawal severity (assessed with self-report symptoms and cognitive performance).

Exploratory Aim#2: To examine the impact of plasma nicotine levels and rate of nicotine metabolism (measured by plasma hydroxycotinine/cotinine ratio) on the dose-effect curves for the main study outcomes.

Exploratory Aim#3: To examine sex differences for the main study outcomes.

5. Background:

Nicotine control policies to reduce the addictive potential of tobacco products:

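### H1A predicts an ordered decline across delivery rates, but the plan does not say whether the unordered condition effect or one of several overlapping shape contrasts decides it

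*Combined protocol and SAP*

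**What the plan says.** Hypothesis #1A (section 4) is directional and ordered: "Positive subjective effects of nicotine will gradually decline with slower delivery rates, with minimal effects of nicotine delivery rate on urges to smoke".

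Section 9, Overview, describes five sessions, each with "either saline or nicotine at four different infusion rates". The rates are 0.024, 0.048, 0.096 and 0.24 mcg/kg/s.

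Section 10 models the peak change on each of two DEQ items (liking and good effects) with menthol preference between subjects and "nicotine delivery condition as a within-subject factor and their interaction". It continues: "We anticipate statistically significant main effects of menthol-preference, nicotine delivery rate", together with an interaction. The next step is introduced with "To better understand the dose effects of nicotine delivery rate and whether they are moderated by menthol preference" and consists of contrasts among the four rates "to test whether there is an indication of significant linear, quadratic, linear on log-scale or sigmoidal dose-response relationships across, or within menthol-preference groups". Curves suggested by the contrasts are then fitted with continuous dose and compared by AIC.

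The sample-size rationale gives the only multiplicity statement: 0.025, Bonferroni for two outcome measures. It claims 80% power with 28 per group for the within-subject rate effect at f>0.5.

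**The concern.** H1A is a claim about a trend across four ordered rates. The main effect of a categorical factor ignores order, so any pattern of means can make it significant. The shape contrasts do use order, but there are four of them, each tested overall and in two groups: 4 × 3 = 12 tests per item, 24 over both items. Section 10 gives no coefficients, no primary contrast, no requirement that the overall test be significant first, and no critical value that covers shapes or groups.

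An analyst could therefore report H1A as supported on the main effect, on whichever shape reached significance, or on a result in one group only. The dose-effect curve is the study's primary aim and is meant to yield a threshold rate, so the choice bears on the main conclusion.

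**Working it through.** **Inputs from the plan.** Four nicotine rates plus saline; 28 per group after dropout, so N=56; alpha 0.025 per item (0.05/2), taken as two-sided because the plan does not say; f=0.5.

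**Assumed inputs.** The plan gives no sigmoid coefficients. Hill curves with ED50 from 0.048 to 0.12 and slope from 2 to 4 were used, hence the ranges below.

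**1. The plan's own power figure.** With λ = f²N = 0.25 × 56 = 14 and error df = (56 − 2)(m − 1):
- four rates (m=4; df 3, 162): power 82.5%
- five conditions including saline (m=5; df 4, 216): power 78.5%

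This brackets the stated 80%, so λ = f²N is taken as the plan's convention. If λ is instead f²N·m/(1 − ρ), power is about 100%.

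**2. If an ungated contrast decides.** Unit contrasts on the four rates were simulated under a flat curve, each tested at 0.025. The three monotone contrasts overlap strongly. Linear and log-linear correlate 0.95, and over linear, log-linear and sigmoid the correlations run from 0.79 to 0.995. Error therefore grows less than independence would suggest (1 − 0.975⁴ = 9.6%; 1 − 0.975¹² = 26.2%).

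| Event under a flat curve, one item | Rate | Reference |
|---|---|---|
| Any of 4 overall contrasts significant | 5.7-6.2% | 2.5% |
| Any of 12 (overall and both groups) | 13-14% | 2.5% |
| Overall linear, log-linear or sigmoid significant in H1A's direction | 1.7-2.1% | 1.25% for one trend |

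**3. If the omnibus test over the four rates decides or gates.** Any-of-4 falls to 1.7-1.8% and any-of-12 to 1.9-2.0%, so nothing is inflated when neither group has a rate effect. The cost is power. At λ=14 a matched one-df trend has 93%, against 82% (3 df) or 78% (4 df). For 80% power the noncentrality must be 9.65 for the trend, 13.29 for 3 df and 14.43 for 4 df, ratios of 1.38 and 1.49.

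**4. If the factor includes saline.** Suppose nicotine differs from saline by d SD and rate has no effect. The squared deviations of the five condition means sum to 0.8d², so with an assumed within-subject correlation of 0.5, λ = 56 × 0.8d²/0.5:
- d=0.4: λ=14.3; the five-level test is significant about 80% of the time
- d=0.6: λ=32.3; at least 99.5%

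Used as a gate, it leaves any-of-4 at 5.6-5.8% and any-of-12 at 12-12.4% for d=0.4. For d=0.6 or more the figures are 5.7-5.9% and 13-14%, essentially the ungated rates.

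**The case against.** The strongest reply is that the contrasts are follow-up. They are introduced as an aid to understanding, they look for an indication, and AIC, not significance, chooses the curve. That is a fair reading of the text. It also answers the complaint that overlapping contrasts cannot identify a shape, because the plan does not ask them to. But on this reading H1A rests on the unordered main effect, which does not test order and, with saline in the factor, may not test rate at all.

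Four stronger inferences are tempting, and the documents do not support them.

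- *The plan both loses power and inflates error.* These mostly belong to different readings. Power is lost only if the omnibus test decides or gates, since the linear and log-linear contrasts are already one-df trend tests. Error inflates if the contrasts are ungated, or if the gate includes saline. A gate over the four rates removes inflation under the complete null, though it would not protect contrasts within one group when only the other group responds to rate.
- *H1A has a false-positive risk of 13% or more.* Eight of the twelve contrasts per item are within groups, where the plan's purpose is moderation, and a significant quadratic alone does not support H1A. Counting all 24 tests over both items gives 21-26%, but the reference there is 5% and few of those events would be read as a decline with slower delivery.
- *There is no error control.* There is: Bonferroni for two outcomes. It does not reach shapes or groups.
- *The study is underpowered for rate.* At the plan's own f=0.5 the omnibus has 78-82% power, and 93-95% at f=0.6. Rises small enough to make the omnibus look weak do not appear in the documents.

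It can also be said that log-rate is one choice among several, which is true. The need is for a stated trend, not for that particular one.

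**Conclusion.** The point stands in a limited form: the plan does not name the test of H1A, and each candidate has a defect. Ungated overall contrasts carry 5.7-6.2% per item against 2.5%, although the excess in H1A's own direction is modest (1.7-2.1% against 1.25%). An omnibus test over the four rates controls error under the complete null but has less power than a matched trend (82% against 93%; 78% on 4 df). An omnibus test that includes saline can be significant because of nicotine alone and then says nothing about rate.

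The error rates depend on the assumed sigmoid and two-sided testing, the power comparison on λ = f²N, and the saline result on a correlation of 0.5 and differences of 0.4-0.6 SD. That section 10 names no deciding test depends on none of these.

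**What to change.** State in section 10 that H1A is tested, for each of the two DEQ items at 0.025, by one pre-specified trend contrast over the four nicotine rates, excluding saline and pooling both preference groups. Give the coefficients. For a log-rate trend they are the centred natural logarithms of the rates: −1.096, −0.402, 0.291 and 1.207 from slowest to fastest.

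Label the other shapes, the within-group contrasts and the AIC fits exploratory. If all four shapes are to be tested, use a joint max-contrast critical value of about 2.58-2.62 (depending on the sigmoid chosen) for the overall set. State also whether saline is a level of the condition factor.

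The cost is wording only: no added subjects or procedures. Where the 3-df omnibus has 80% power, a single trend has 92% if its shape is right and 84-90% under the other monotone shapes tried; the joint four-contrast test has 86-87%. The price is less power for a non-monotone pattern, which H1A does not predict. The change does not address the second half of H1A, the minimal effect on urges, which needs its own criterion.
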